5.1 Treatment Plan

Patritumab deruxtecan (U3-1402) 5.6 mg/kg IV will be administered Day 1 Q3W. Patritumab deruxtecan will be prepared and administered via IV infusion according to the details in [Section 8.1.2](#).

5.2 Treatment Duration

The **start of the study** is defined as the date when the first patient in the whole study signs informed consent.

The **end of the study** is defined as the date of the last visit (including all follow-up visits) of the last patient in the whole study.

CONFIDENTIAL

5.3 Concomitant Medications

Patients will be asked about prior medications during screening and instructed not to take any additional medications during the course of the study without prior consultation with the study team. At each visit, the patient will be asked about any new medications he or she is taking or has taken after the start of the study drug.

5.3.1 Permitted Concomitant Medications

Premedication with anti-emetics is recommended.

Medications may be administered for maintenance of existing conditions prior to study enrollment or for a new condition that develops while on study, including but not limited to the following:

- Bisphosphonate (such as pamidronate or zoledronic acid) use or denosumab for pain management and palliation of bone metastases, or treatment of osteoporosis, as recommended according to practice guidelines
- Receptor activator of nuclear factor kappa-B ligand (RANKL) inhibitor use, as recommended according to practice guidelines
- Hematopoietic growth factors used for prophylaxis or treatment
- Patients taking warfarin should be monitored regularly for changes in PT or INR.

Supportive care and other medications considered necessary for the patient's safety and well-being may be given at the discretion of the Investigator, with the exception of those listed in Section 5.3.2.

5.3.2 Prohibited Concomitant Medications

The following treatments are prohibited while in this study:

- No other investigational therapy should be given to patients. No anticancer agents other than the study treatments should be given to patients. If such agents are required for a patient, then the patient must first be withdrawn from the study.
- Live virus vaccination (beginning from 28 days prior to Cycle 1 Day 1)
- Radiotherapy, except for palliative radiation (as long as the radiation field does not include the only measurable lesion or does not interrupt treatment for more than 28 days from the planned date of administration [i.e., 49 days from the last infusion date of patritumab deruxtecan])
- Radiotherapy to the thorax is also prohibited once a patient is screened and enrolled into the study.
- Concomitant use of chronic systemic (intravenous (IV) or oral) corticosteroids (i.e., >10 mg prednisone or equivalent) or other immunosuppressive medications except for managing AEs
- Herbal preparations/medications that could potentially interact with patritumab deruxtecan may not be allowed throughout the study. Any use of these substances will require discussion with the Medical Monitor. These herbal medications include, but are not limited

CONFIDENTIAL

to: St. John's wort, kava, ephedra (ma huang), ginkgo biloba, dehydroepiandrosterone, yohimbe, saw palmetto, cannabis and other medical marijuana products, and ginseng. Patients may need to stop using these herbal medications ≥ 7 days prior to the first dose of the study drug.

5.3.3 Restricted Therapies/Products

Patients who wear contact lenses must discontinue wearing their lenses if they have any mild to moderate symptoms (CTCAE Grade ≤ 2) while receiving treatment until at least 1 week after symptoms have resolved. If a patient has a recurrence of eye symptoms or experiences any severe (CTCAE Grade ≥ 3) ocular events, they must discontinue wearing their contact lenses until at least 1 week after treatment is permanently discontinued. Patients must not use any eye drops or ointment for treatment of eye symptoms, unless approved by a study doctor, at any time during the study and ≥ 1 week after permanent discontinuation of study treatment.

6. DOSE MODIFICATIONS

If toxicity occurs, the toxicity will be graded using the NCI CTCAE Version 5.0, and appropriate supportive care treatment will be administered to decrease the signs and symptoms thereof. Dose adjustments will be based on the organ system exhibiting the greatest degree of toxicity.

Doses of patritumab deruxtecan will be modified based on hematologic and non-hematologic toxicity. If dose reductions are necessary, they will be permanent for the remainder of the treatment. Any patient requiring a toxicity-related dose delay of more than 18 weeks (126 days) from the last patritumab deruxtecan dose must be discontinued from the study, unless discussed with the Medical Monitor for extenuating circumstances. During the time of any dose delay, scheduled CT/MRI scans should continue as per protocol, and subjects should fulfill all of the following criteria:

- Study drug may be resumed with confirmation of continued benefit per RECIST 1.1. Scans should be performed at the frequency defined per protocol while the drug is being held.
- At minimum, 1 restaging scan must be done within 6 weeks prior to restarting the study drug.
- Investigational product is restarted within the guidance of the treatment management guidelines for patritumab deruxtecan, if appropriate.
- No prohibited concomitant medications have been administered since the last dose of patritumab deruxtecan.

If toxicities occur that are \leq Grade 2, they should be managed symptomatically, if possible, and the patient should be re-treated without a dose reduction. If toxicities occur that are \geq Grade 3, treatment should be withheld until resolution to \leq Grade 1 or to the baseline value (if the baseline value was $>$ Grade 1). Treatment should then be re-instituted, if medically appropriate, at the next lower dose level (see Table 2).

The dose level reductions to be used in this study are presented in Table 2.

CONFIDENTIAL

Table 2 Dose Level Modifications

Dose Level	Patritumab deruxtecan
Starting Dose	5.6 mg/kg
Dose Level -1	4.8 mg/kg
Dose Level -2	3.2 mg/kg

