6.1 Dose Modifications Due to Hematologic Toxicity

Dose reductions or holds and initiation of supportive care are allowed as clinically indicated by the treating physician. Patients whose treatment is delayed due to toxicity will discontinue study drug or will proceed with treatment when toxicity has improved (as long as the toxicity resolves within 126 days from the time of the last administration of patritumab deruxtecan) according to the dose modifications below.

Table 3 Dose Modifications Due to Hematologic Toxicities

	Worst Toxicity NCI CTCAE Version 5.0 Grade (unless otherwise specified)	Schedule Modification for patritumab deruxtecan
Blood and lymphatic system disorders		
Neutrophil count decreased	Grade 3 (500 - <1000/mm ³ ; 0.5-1 × 10 ⁹ /L)	Delay dose until resolved to ≤Grade 2, then resume patritumab deruxtecan.
	Grade 4 (<500/mm ³ ; <0.5 × 10 ⁹ /L)	Delay dose until resolved to ≤Grade 2, study treatment may be resumed after discussion and agreement between the Investigator and Medical Monitor. If treatment is resumed, then reduce by at least 1 dose level.
Febrile neutropenia (ANC <1000/mm³; <1 × 10⁹/L, fever >38.3°C or a sustained temperature of ≥38°C for more than 1 hour)	Grade 3 and 4	Delay dose until resolved, then reduce patritumab deruxtecan by 1 dose level and resume. Administration of G-CSF as prophylaxis for all subsequent cycles is recommended.

CONFIDENTIAL

	Worst Toxicity NCI CTCAE Version 5.0 Grade (unless otherwise specified)	Schedule Modification for patritumab deruxtecan
Anemia	Grade 3 (Hgb <8.0 g/dL)	Delay dose until resolved to \leq Grade 2 or baseline, then resume patritumab deruxtecan. For recurrent anemia, delay dose until resolved \leq Grade 2 or baseline, then reduce patritumab deruxtecan dose by 1 level. Consider transfusion according to institutional guidelines.
	Grade 4 (Life-threatening consequences; urgent intervention indicated)	Delay dose until resolved to \leq Grade 2 or baseline, then reduce patritumab deruxtecan dose by 1 level. Consider transfusion according to institutional guidelines.
Platelet count decreased	Grade 3 ($<50 - 25 \times 10^9/L$)	Delay dose until resolved to \leq Grade 1, then: 
 • If resolved in ≤ 14 days, resume patritumab deruxtecan. • If resolved in >14 days, patritumab deruxtecan may be resumed. Consider reducing patritumab deruxtecan by 1 dose level. Consider transfusion according to institutional guidelines.

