	Grade 4 ($<25 \times 10^9/L$)	Delay dose until resolved to \leq Grade 1, then reduce patritumab deruxtecan by 1 dose level. Consider transfusion according to institutional guidelines.
Lymphocyte Count Decreased	Grade 4 ($<0.2 \times 10^9/L$)	Delay dose until resolved to \leq Grade 2, then: 
 • If resolved in ≤ 14 days, resume patritumab deruxtecan. • If resolved in >14 days, then reduce patritumab deruxtecan by 1 dose level.

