Vomiting	Grade 3 (Tube feeding, TPN, or hospitalization indicated)	Delay patritumab deruxtecan until resolved \leq Grade 1, and consider treatment with antiemetics and / or corticosteroids as per Investigator's judgement and local practice/guidelines, then: 
 • If resolved to \leq Grade 1 in ≤ 7 days, resume patritumab deruxtecan. • If resolved to \leq Grade 1 in > 7 days, then reduce patritumab deruxtecan by 1 dose level.
	Grade ≥ 4	Discontinue patient from patritumab deruxtecan.
Premedicate with a two or three drug combination regimen (e.g., dexamethasone with either a 5-HT3 receptor antagonist or an NK-1 receptor antagonist as well as other drugs as indicated) for prevention of chemotherapy-induced nausea and vomiting (CINV).		
Diarrhea/Colitis	Grade 3	Delay patritumab deruxtecan until resolved \leq Grade 1, and consider treatment per local practice/guidelines, then: 
 • If resolved to \leq Grade 1 in ≤ 7 days, resume patritumab deruxtecan. • If resolved to \leq Grade 1 in > 7 days, then reduce patritumab deruxtecan by 1 dose level.
	Grade 4 (Life-threatening consequences; urgent intervention indicated)	Discontinue patient from patritumab deruxtecan.
Mucositis oral	Grade 3	Delay patritumab deruxtecan until resolved \leq Grade 1, and consider treatment per local practice/guidelines, then: 
 • If resolved to \leq Grade 1 in ≤ 14 days, resume patritumab deruxtecan. • If resolved to \leq Grade 1 in > 14 days, then reduce patritumab deruxtecan by 1 dose level.

CONFIDENTIAL

	Worst Toxicity NCI CTCAE Version 5.0 Grade (unless otherwise specified)	Schedule Modification for Patritumab deruxtecan
	Grade 4 (Life-threatening consequences; urgent intervention indicated)	Discontinue patient from patritumab deruxtecan.
Other adverse events (Non-laboratory or Laboratory)	Grade 3	Delay patritumab deruxtecan until resolved \leq Grade 1, or baseline, then: 
 • If resolved in ≤ 7 days, resume patritumab deruxtecan. • If resolved to in > 7 days, then reduce patritumab deruxtecan by 1 dose level.
	Grade 4 (Life-threatening consequences; urgent intervention indicated)	Discontinue patient from patritumab deruxtecan.

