6.2.2 Specific Recommendations for Liver Function Test Abnormalities

For patients with Grade 3 liver enzyme elevations (AST/ALT), patritumab deruxtecan should be held until the values recover to \leq Grade 1. Patients with an elevation of ALT/AST $\geq 3 \times$ ULN in conjunction with a bilirubin $\geq 2 \times$ ULN may remain in the study if a correctable, non-drug-related cause of the liver test evaluations can be documented; otherwise, the patient must be discontinued from the study.

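### Section 6's general rule for Grade 3 or worse toxicity conflicts with many rows of Tables 3 and 4, and no sentence says which text governs

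*Combined protocol and SAP*

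**What the plan says.** **Section 6 (general text).** For events of Grade 2 or lower, "they should be managed symptomatically, if possible, and the patient should be re-treated without a dose reduction". For Grade 3 or worse, the drug is withheld to Grade 1 or lower, or to baseline if baseline was above Grade 1. Then: "Treatment should then be re-instituted, if medically appropriate, at the next lower dose level (see Table 2"). Any reduction lasts for the rest of treatment. Table 2 sets the levels at 5.6, 4.8 and 3.2 mg/kg.

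**Table 3 (Section 6.1).**
- Neutrophil count decreased, Grade 3: "Delay dose until resolved to ≤Grade 2, then resume patritumab deruxtecan".
- Anemia, Grade 3: a first event resumes at Grade 2 or lower, or baseline. Reduction comes only with recurrence: "For recurrent anemia, delay dose until resolved" to that level, then reduce.
- Platelet count decreased, Grade 3: resume if resolved within 14 days. If slower, "patritumab deruxtecan may be resumed. Consider reducing patritumab deruxtecan by 1 dose level".
- "Lymphocyte Count Decreased" appears only at Grade 4. It resumes if resolved within 14 days and is reduced if slower.

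**Table 4 (Section 6.2).** Grade 3 fatigue, ocular events, AST/ALT, nausea, vomiting, diarrhea/colitis, oral mucositis and the row "Other adverse events (Non-laboratory or Laboratory") resume if resolved within 7 or 14 days, depending on the row. They are reduced by one level only if slower.

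**Section 6.2.2.** For Grade 3 AST/ALT, "patritumab deruxtecan should be held until the values recover to" Grade 1 or lower.

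**The concern.** A site treating a Grade 3 event finds two current instructions. The general text requires a lower dose on restart. The row for that event often requires none, and sometimes allows restart at a higher residual grade. Because reductions are permanent, the choice affects every later cycle.

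The stake is exposure. Section 1.3 says 5.6 mg/kg was selected partly because it is predicted to improve ORR over 4.8 mg/kg, which is Dose Level -1. ORR is one of the two primary measures. The Synopsis plans about 10 sites, so divergent reading is a practical possibility, and it is also a patient-safety matter.

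**Working it through.** The plan gives no figure to reproduce. The check sets the texts side by side, with one count and one ratio.

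**1. Rows that cover Grade 3.** I counted the graded rows of Tables 3 and 4 that apply at Grade 3. The count includes heart failure (Grade 2 and above), ILD Grade 3 and 4, and the separate AST/ALT row for liver-metastasis patients with a raised baseline.

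| | Resumption with no required reduction | Reduction or discontinuation |
|---|---|---|
| Table 3 | neutrophils, first anemia, platelets (3) | febrile neutropenia (1) |
| Table 4 | fatigue, ocular, AST/ALT (2 rows), nausea, vomiting, diarrhea/colitis, oral mucositis, other events (9) | infusion reaction, heart failure, QTc (reduction only if attributed to study drug), ILD, creatinine, bilirubin (6) |
| Total | 12 | 7 |

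So 12 of 19 rows depart from the Section 6 rule on restart dose. All 9 in Table 4 are conditional on time: 14 days for fatigue, nausea and mucositis, and 7 days for the rest. The Grade 4 lymphocyte row also allows resumption without reduction, if resolved within 14 days.

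**2. Recovery threshold.** Section 6 asks for Grade 1 or lower, or baseline. The neutrophil, anemia, lymphocyte and ocular rows accept Grade 2 or lower.

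**3. Grade 2 or lower.** Section 6 re-treats without reduction. Table 4 reduces for heart failure from Grade 2. It also reduces for Grade 2 bilirubin that takes more than 7 days to resolve in patients without Gilbert's syndrome or liver metastases.

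**4. Grade 4.** Section 6 foresees restart at a lower level, if medically appropriate. Table 4 discontinues at Grade 4 for, among others, ocular events, creatinine, AST/ALT, bilirubin, diarrhea/colitis, oral mucositis and other events. One text leaves a judgement; the other does not.

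**5. AST/ALT recovery.** Section 6.2.2 requires Grade 1 or lower without exception. Table 4 uses the baseline level for liver-metastasis patients who start above 3 x ULN. Section 6 itself allows recovery to baseline, so this conflict lies only between Section 6.2.2 and Table 4.

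**6. Is precedence stated?** Section 6 bases adjustment on the organ system with the greatest toxicity. That chooses among organ systems and does not rank the general text against the tables. Section 6.1 directs the reader to Table 3, and Section 6.2.1 sends confirmed ILD to Table 4. Neither says that the tables override Section 6.

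**7. Size of the dose step.** From Table 2: 1 − 4.8/5.6 = 0.8/5.6 = 0.143, a 14.3% lower dose.

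**The case against.** The best reply is that specific tables override a general paragraph, and the document leans that way. Section 6.1 tells sites to proceed by its table, Section 6.2.1 and Appendix E refer sites to Table 4, and Section 6 requires restart within the treatment management guidelines. Section 6 says should, and qualifies it by medical appropriateness. Section 6.1 leaves holds and reductions to the treating physician as clinically indicated. This makes the tables the more natural reading, but it is not a written rule. The qualifier in Section 6 governs whether to restart; it offers no restart at an unchanged dose.

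A reader might go further than the documents allow in four ways.

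- **That Section 6 has no events left to govern, because Table 4 has a catch-all row.** That row sits in the non-hematologic table, and Table 3 has none. White blood cell count decreased has no row in Table 3, although Section 1.1.3 reports it at Grade 3 or higher in 21 of 144 patients (14.6%). Lymphocyte decreases are listed only at Grade 4. Section 6 could be the default for such events.
- **That Grade 2 ILD is a further conflict.** Section 6.2.1 already sends confirmed ILD to Table 4.
- **That the tables say to resume at the same dose.** They say only to resume. The unchanged dose is inferred from the contrast with rows and branches that say to reduce.
- **That the conflict can be sized from the cited phase I/II study.** There, 92/144 (63.9%) had a Grade 3 or higher event and 22/144 (15.3%) had an event-related dose reduction. Those patients had mixed doses under dose rules not given here. The 63.9% also includes events for which the tables reduce or discontinue. Likewise, ORR of 6/15 at 4.8 mg/kg and 9/15 at 6.4 mg/kg is too small a comparison to carry weight (two-sided Fisher p = 0.47), and it compares assigned doses, not a reduction during treatment.

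**Conclusion.** The contradiction stands, in current operative dosing text. Section 6 and 12 of the 19 Grade 3 rows differ on whether a reduction is required. Some rows also differ on the recovery threshold, and there are narrower conflicts at Grade 2, at Grade 4 and in AST/ALT recovery. The count rests on reading resume as no required reduction, and for the Table 4 rows on resolution within the stated 7 or 14 days.

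The only size that the documents support is the dose step: 14.3% at the first reduction, permanent. That sites could deliver different exposure follows from the text. How many patients would be affected, and by how much ORR would move, cannot be computed. In the cited study, Grade 3 or higher neutrophil (25.7%), platelet (22.2%) and anemia (17.4%) events were common. Those figures mix doses and do not separate Grade 3 from Grade 4, so they show relevance and do not measure impact. This review takes no position on which rule is clinically right.

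**What to change.** Reconcile the Section 6 paragraph, Tables 3 and 4 and Section 6.2.2, and add a sentence stating the order of precedence. That sentence should also cover hematologic events with no row in Table 3, such as white blood cell count decreased and Grade 3 lymphocyte count decreased. The medical team decides each rule. Notify sites by memo so that all work from the same text until the amendment is in force.

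The cost is amendment wording and one memo. Section 10.4.3 lists no dose-reduction summary; adding one by study part would show how the rules were applied, but it is optional and not needed to resolve the contradiction.

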6.1 Dose Modifications Due to Hematologic Toxicity

Dose reductions or holds and initiation of supportive care are allowed as clinically indicated by the treating physician. Patients whose treatment is delayed due to toxicity will discontinue study drug or will proceed with treatment when toxicity has improved (as long as the toxicity resolves within 126 days from the time of the last administration of patritumab deruxtecan) according to the dose modifications below.

Table 3 Dose Modifications Due to Hematologic Toxicities

	Worst Toxicity NCI CTCAE Version 5.0 Grade (unless otherwise specified)	Schedule Modification for patritumab deruxtecan
Blood and lymphatic system disorders		
Neutrophil count decreased	Grade 3 (500 - <1000/mm ³ ; 0.5-1 × 10 ⁹ /L)	Delay dose until resolved to ≤Grade 2, then resume patritumab deruxtecan.
	Grade 4 (<500/mm ³ ; <0.5 × 10 ⁹ /L)	Delay dose until resolved to ≤Grade 2, study treatment may be resumed after discussion and agreement between the Investigator and Medical Monitor. If treatment is resumed, then reduce by at least 1 dose level.
Febrile neutropenia (ANC <1000/mm³; <1 × 10⁹/L, fever >38.3°C or a sustained temperature of ≥38°C for more than 1 hour)	Grade 3 and 4	Delay dose until resolved, then reduce patritumab deruxtecan by 1 dose level and resume. Administration of G-CSF as prophylaxis for all subsequent cycles is recommended.

CONFIDENTIAL

	Worst Toxicity NCI CTCAE Version 5.0 Grade (unless otherwise specified)	Schedule Modification for patritumab deruxtecan
Anemia	Grade 3 (Hgb <8.0 g/dL)	Delay dose until resolved to \leq Grade 2 or baseline, then resume patritumab deruxtecan. For recurrent anemia, delay dose until resolved \leq Grade 2 or baseline, then reduce patritumab deruxtecan dose by 1 level. Consider transfusion according to institutional guidelines.
	Grade 4 (Life-threatening consequences; urgent intervention indicated)	Delay dose until resolved to \leq Grade 2 or baseline, then reduce patritumab deruxtecan dose by 1 level. Consider transfusion according to institutional guidelines.
Platelet count decreased	Grade 3 ($<50 - 25 \times 10^9/L$)	Delay dose until resolved to \leq Grade 1, then: 
 • If resolved in ≤ 14 days, resume patritumab deruxtecan. • If resolved in >14 days, patritumab deruxtecan may be resumed. Consider reducing patritumab deruxtecan by 1 dose level. Consider transfusion according to institutional guidelines.
	Grade 4 ($<25 \times 10^9/L$)	Delay dose until resolved to \leq Grade 1, then reduce patritumab deruxtecan by 1 dose level. Consider transfusion according to institutional guidelines.
Lymphocyte Count Decreased	Grade 4 ($<0.2 \times 10^9/L$)	Delay dose until resolved to \leq Grade 2, then: 
 • If resolved in ≤ 14 days, resume patritumab deruxtecan. • If resolved in >14 days, then reduce patritumab deruxtecan by 1 dose level.

6.2 Dose Modifications due to Non-Hematologic Toxicity

Table 4 Dose Modifications Due to Non-Hematologic Toxicities

	Worst Toxicity NCI CTCAE Version 5.0 Grade (unless otherwise specified)	Schedule Modification for Patritumab deruxtecan
General disorders and administration site conditions		

CONFIDENTIAL

	Worst Toxicity NCI CTCAE Version 5.0 Grade (unless otherwise specified)	Schedule Modification for Patritumab deruxtecan
Infusion related reaction (e.g., same reduced rate as previous infusion)	Grade 1 (Mild transient reaction; infusion interruption not indicated; intervention not indicated)	If infusion related reaction (such as fever and chills, with and without nausea/vomiting, pain, headache, dizziness, dyspnea, hypotension) is observed during administration, the infusion rate should be reduced by 50% and patients should be closely monitored. If no other reactions appear, the subsequent infusion rate could be resumed at the initial planned rate.
	Grade 2 (Therapy or infusion interruption indicated but responds promptly to symptomatic treatment (e.g. antihistamines, nonsteroidal anti-inflammatory drugs [NSAIDs], narcotics, IV injection fluids); prophylactic medications indicated for ≤24 hours)	Patritumab deruxtecan infusion should be interrupted. Symptomatic treatment (e.g., antihistamines, NSAIDs, narcotics, IV fluids) should be started. If the event resolves or improves to Grade 1, infusion can be re-started at a 50% reduced infusion rate. Upon restart, if Grade 2 symptoms recur, no further patritumab deruxtecan should be administered at that visit. The amount of patritumab deruxtecan infused must be recorded in the eCRF. Subsequent infusions should be conducted at the 50% reduced infusion rate.
	Grade 3 (Prolonged [e.g. not rapidly responsive to symptomatic medication and/or brief interruption of infusion]; recurrence of symptoms following initial improvement; hospitalization indicated for clinical sequelae)	Administration of patritumab deruxtecan should be discontinued immediately and permanently. Urgent intervention indicated. Antihistamines, steroids, epinephrine, bronchodilators, vasopressors, IV fluid therapy, oxygen inhalation etc., should be administered as clinically indicated.
	Grade 4 (Life-threatening consequences; urgent intervention indicated)	
Fatigue/ Asthenia/Malaise	Grade 3	Delay dose until resolved to ≤ Grade 1 or baseline, then: 
 • If resolved to ≤ Grade 1 or baseline in ≤14 days, resume patritumab deruxtecan. • If resolved to ≤ Grade 1 or baseline in >14 days, then reduce patritumab deruxtecan by 1 dose level.
Cardiac disorders		

CONFIDENTIAL

	Worst Toxicity NCI CTCAE Version 5.0 Grade (unless otherwise specified)	Schedule Modification for Patritumab deruxtecan
Heart failure	Grade ≥ 2 (Symptoms with moderate activity or exertion)	Cardiologist consultation as necessary. Delay dose until resolved to \leq Grade 1, then reduce patritumab deruxtecan by 1 dose level.
Ejection fraction decreased	Decrease in LVEF 10% - 20% (absolute value), but LVEF $>45\%$	Continue patritumab deruxtecan.
	LVEF 40% - $\leq 45\%$ and decrease is $<10\%$ (absolute value) from baseline	Continue patritumab deruxtecan. Repeat LVEF assessment within 3 weeks.
	LVEF 40% - $\leq 45\%$ and decrease is $\geq 10\%$ to 20% (absolute value) from baseline	Delay patritumab deruxtecan. Repeat LVEF assessment within 3 weeks. If LVEF has not recovered to within 10% (absolute value) from baseline, discontinue patient from study treatment.
	LVEF $<40\%$ or $>20\%$ (absolute value) drop from baseline	Delay patritumab deruxtecan. Repeat LVEF assessment within 3 weeks. If LVEF $<40\%$ or $>20\%$ (absolute value) drop from baseline is confirmed, discontinue patritumab deruxtecan. Cardiologist consultation as necessary.
Electrocardiogram QT corrected interval prolonged	Grade 3 (Average QTcF ≥ 501 ms; >60 ms change from baseline)	Delay patritumab deruxtecan until resolved to \leq Grade 1 (QTcF ≤ 480 ms). Determine if another medication the patient was taking may be responsible and can be adjusted or if there are any changes in serum electrolytes that can be corrected. If QTcF prolongation is attributed to patritumab deruxtecan, then reduce patritumab deruxtecan by 1 dose level. Cardiologist consultation as necessary.
	Grade 4 (Torsade de pointes; polymorphic ventricular tachycardia; signs/symptoms of serious arrhythmia)	Discontinue patient from patritumab deruxtecan. Cardiologist consultation as necessary.

CONFIDENTIAL

	Worst Toxicity NCI CTCAE Version 5.0 Grade (unless otherwise specified)	Schedule Modification for Patritumab deruxtecan
Respiratory, thoracic and mediastinal disorders		
ILD	See next column	
If a patient develops radiographic changes potentially consistent with ILD or develops an acute onset of new or worsening pulmonary or other related signs/symptoms such as dyspnea, cough or fever, rule out ILD.
 
If ILD is suspected, delay patritumab deruxtecan dosing pending further evaluation and start corticosteroid treatment promptly per consensus statement^a unless clinically contraindicated.
 
Evaluations must include CT (preferably high-resolution CT), and pulmonologist consultation (when the Investigator is not a pulmonologist). The following evaluations should also be obtained, as indicated:
 
 • Infectious disease consultation as clinically indicated • Blood culture and CBC (other blood tests could be considered as needed) • Bronchoscopy and bronchoalveolar lavage if clinically indicated and feasible • Pulmonary function tests • Pulse oximetry (SpO₂) • Arterial blood gases, as clinically indicated • Diffusing capacity of the lungs for carbon monoxide (DLCO), as clinically indicated • One blood sample collection for PK analysis as soon as ILD/pneumonitis is suspected, if feasible • Other tests, as clinically indicated 
If a non-inflammatory/infectious etiology is confirmed by the Investigator, treat accordingly and resumption of patritumab deruxtecan may occur after discussion between the Investigator and Sponsor.
 
All events of ILD regardless of severity or seriousness will be followed until resolution including after drug discontinuation.

^a Kubo K, Azuma A, Kanazawa M, et al. Japanese Respiratory Society Committee. Consensus statement for the diagnosis and treatment of drug-induced lung injuries. Respir Investig. 2013; 51(4):260-77.
		

CONFIDENTIAL

	Worst Toxicity NCI CTCAE Version 5.0 Grade (unless otherwise specified)	Schedule Modification for Patritumab deruxtecan
Respiratory, thoracic and mediastinal disorders - ILD		
	Grade 1	
The administration of patritumab deruxtecan must be delayed. Patritumab deruxtecan can be restarted only if the event is fully resolved to Grade 0:
 
 • If resolved in ≤ 28 days from day of onset, maintain dose. • If resolved in > 28 days from day of onset, reduce dose 1 level. 
Toxicity Management:
 
 • Monitor and closely follow-up in 2 to 7 days for onset of clinical symptoms and pulse oximetry. • Consider follow-up imaging in 1-2 weeks (or as clinically indicated). • Consider starting systemic steroids (e.g. at least 0.5 mg/kg/day prednisone or equivalent) until improvement, followed by gradual taper over at least 4 weeks. • If there is worsening of diagnostic observations despite initiation of corticosteroids, then follow Grade 2 guidelines (if patient is asymptomatic, then patient should still be considered as Grade 1 even if steroid treatment is given).

CONFIDENTIAL

	Worst Toxicity NCI CTCAE Version 5.0 Grade (unless otherwise specified)	Schedule Modification for Patritumab deruxtecan
Respiratory, thoracic and mediastinal disorders - ILD		
	Grade 2	
Permanently discontinue patient from study treatment.
 
Toxicity Management:
 
 • Promptly start systemic steroids (e.g., at least 1 mg/kg/day prednisone or equivalent) for a minimum of 14 days or until complete resolution of clinical symptoms and chest CT findings, followed by gradual taper over at least 4 weeks. • Monitor symptoms closely. • Re-image as clinically indicated. • If worsening or no improvement in clinical or diagnostic observations in 5 days, 
 – Consider increasing dose of steroids (e.g., 2 mg/kg/day prednisone or equivalent) and administration may be switched to IV (e.g., methylprednisolone). – Re-consider additional work-up for alternative etiologies as described above. – Escalate care as clinically indicated.
	Grade 3 and 4	
Permanently discontinue patient from study treatment.
 
Toxicity Management:
 
 • Hospitalization required. • Promptly initiate empiric high-dose methylprednisolone IV treatment (e.g., 500-1000 mg/day for 3 days), followed by at least 1.0 mg/kg/day of prednisone (or equivalent) for a minimum of 14 days or until complete resolution of clinical symptoms and chest CT findings, followed by gradual taper over at least 4 weeks. • Re-image as clinically indicated. • If still no improvement within 3 to 5 days, 
 – Re-consider additional work-up for alternative etiologies as described above. – Consider other immunosuppressants and/or treat per local practice.

CONFIDENTIAL

	Worst Toxicity NCI CTCAE Version 5.0 Grade (unless otherwise specified)	Schedule Modification for Patritumab deruxtecan
Eye disorders		
Ocular	Grade 3	Delay dose until resolved to \leq Grade 2, then: 
 If resolved in ≤ 7 days, resume patritumab deruxtecan. If resolved in > 7 days, then reduce patritumab deruxtecan by 1 dose level. Ophthalmologist consultation as necessary.
	Grade 4	Discontinue patient from patritumab deruxtecan. Ophthalmologist consultation as necessary.
Renal and urinary disorders		
Creatinine increased	Grade 3 ($> 3.0 \times$ baseline; $> 3.0-6.0 \times$ ULN)	Delay dose until resolved to \leq Grade 1 or baseline, then reduce patritumab deruxtecan by 1 dose level.
	Grade 4 ($> 6.0 \times$ ULN)	Discontinue patient from patritumab deruxtecan.
Hepatobiliary disorders		
AST or ALT increased without TBL increased	Grade 2 ($> 3.0-5.0 \times$ ULN if baseline was normal; $> 3.0-5.0 \times$ baseline if baseline was abnormal)	Continue patritumab deruxtecan. In patients without liver metastasis, monitor AST/ALT 24 to 72 hours later, and continue regular monitoring until resolution.
	Grade 3 ($> 5.0-20.0 \times$ ULN if baseline was normal; $> 5.0-20.0 \times$ baseline if baseline was abnormal). In patients without liver metastases and patients with liver metastases and baseline level $\leq 3 \times$ ULN.	Delay patritumab deruxtecan dose until resolved to \leq Grade 1, then: 
 If resolved in ≤ 7 days, resume patritumab deruxtecan. If resolved in > 7 days, then reduce patritumab deruxtecan by 1 dose level.
	$> 8.0-20.0 \times$ ULN if baseline was normal; $> 8.0-20.0 \times$ baseline if baseline was abnormal. In patients with liver metastases, if the baseline level was $> 3 \times$ ULN.	Delay patritumab deruxtecan dose until resolved to \leq baseline level, then: 
 If resolved in ≤ 7 days, resume patritumab deruxtecan. If resolved in > 7 days, then reduce patritumab deruxtecan by 1 dose level.

CONFIDENTIAL

	Worst Toxicity NCI CTCAE Version 5.0 Grade (unless otherwise specified)	Schedule Modification for Patritumab deruxtecan
	Grade 4 ($>20.0 \times$ ULN if baseline was normal; $>20.0 \times$ baseline if baseline was abnormal)	Discontinue patient from patritumab deruxtecan. Gastroenterologist or hepatologist consultation as necessary.
TBL increased	Grade 2 (>1.5 - $3.0 \times$ ULN if baseline was normal; >1.5 - $3.0 \times$ baseline if baseline was abnormal)	
If no documented Gilbert's syndrome or liver metastases at baseline, delay patritumab deruxtecan dose until resolved to \leq Grade 1, then:
 
 • If resolved in ≤ 7 days, resume patritumab deruxtecan. • If resolved in >7 days, then reduce patritumab deruxtecan by 1 dose level. 
If documented Gilbert's syndrome or liver metastases at baseline, continue patritumab deruxtecan.

	Grade 3 (>3.0 - $10.0 \times$ ULN if baseline was normal; >3.0 - $10.0 \times$ baseline if baseline was abnormal)	
If no documented Gilbert's syndrome or liver metastases at baseline, delay patritumab deruxtecan dose until resolved to \leq Grade 1, then:
 
 • If resolved in ≤ 7 days, then reduce patritumab deruxtecan by 1 dose level. • If resolved in > 7 days, discontinue patritumab deruxtecan. 
If documented Gilbert's syndrome or liver metastases at baseline, delay patritumab deruxtecan dose until resolved to \leq Grade 2, then:
 
 • If resolved in ≤ 7 days, then reduce patritumab deruxtecan by 1 dose level. • If resolved in >7 days, discontinue patritumab deruxtecan.
	Grade 4 ($>10.0 \times$ ULN if baseline was normal; $>10.0 \times$ baseline if baseline was abnormal)	Discontinue patient from patritumab deruxtecan.

CONFIDENTIAL

	Worst Toxicity NCI CTCAE Version 5.0 Grade (unless otherwise specified)	Schedule Modification for Patritumab deruxtecan
AST or ALT increased and TBL increased	AST or ALT $\geq 3 \times$ ULN with simultaneous TBL $> 2 \times$ ULN	
Delay patritumab deruxtecan until drug-induced liver injury can be ruled out. The Investigator should consult with a gastroenterologist or hepatologist as needed, and the patient should be treated accordingly.
 
Monitor AST/ALT and TBL twice weekly until resolution or return to baseline.
 
It is strongly recommended to perform a full diagnostic workup, to exclude alternative causes such as viral or autoimmune hepatitis, alcoholic liver injury, biliary tract disorders, or hemodynamic abnormalities. Results from diagnostic workup (including, for example: INR, direct bilirubin, serologic tests for hepatitis A, B, and C; alcohol use, ultrasound, MRI, CT scan, concomitant medication use, immunoglobulin levels, ECHO) should be recorded within the eCRF.
 
If drug-induced liver injury is ruled out, the patient should be treated accordingly, and resumption of patritumab deruxtecan may occur after discussion between the Investigator and Sponsor.
 
Patritumab deruxtecan will be permanently discontinued if drug induced liver injury cannot be ruled out from diagnostic workup.

AST or ALT $> 3.0 \times$ ULN (if liver metastases are present, $> 5 \times$ULN) with known hepatitis B and/or hepatitis C infection at baseline	--	
Delay patritumab deruxtecan until reactivation of Hepatitis B and/or Hepatitis C can be ruled out. Perform HBV DNA and/or HCV RNA to rule out reactivation of Hepatitis B and/or Hepatitis C, respectively.
 
Hepatologist and infectious disease consultations are recommended.
 
If reactivation of Hepatitis B and/or Hepatitis C is confirmed, permanently discontinue patritumab deruxtecan.

CONFIDENTIAL

	Worst Toxicity NCI CTCAE Version 5.0 Grade (unless otherwise specified)	Schedule Modification for Patritumab deruxtecan
Gastrointestinal disorders		
Nausea	Grade 3 (Inadequate oral caloric or fluid intake; tube feeding, total parenteral nutrition [TPN], or hospitalization indicated)	Delay patritumab deruxtecan until resolved \leq Grade 1, and consider treatment with antiemetics and/or corticosteroids as per Investigator's judgement and local practice/guidelines, then: 
 • If resolved to \leq Grade 1 in ≤ 14 days, resume patritumab deruxtecan. • If resolved to \leq Grade 1 in > 14 days, then reduce patritumab deruxtecan by 1 dose level.
